7.2.2. Summary Measure

Area under concentration-time curve (AUC[0-48]) and CL_r following single doses of gepotidacin in subjects with normal hepatic function and hepatically impaired subjects.

7.2.3. Population of Interest

The secondary pharmacokinetic analyses will be based on the PK population for plasma and urine PK concentrations, and the PK parameter population for plasma and urine PK parameters and statistical analysis, unless otherwise specified.

7.2.4. Statistical Analyses / Methods

Details of the planned displays are provided in [Appendix 8: List of Data Displays](#) and will be based on GSK Data Standards and statistical principles.

Unless otherwise specified, endpoints/variables defined in Section [7.2.1](#) will be summarized using descriptive statistics, graphically presented (where appropriate) and listed.

7.2.4.1. Statistical Methodology Specification

Endpoint / Variables

 Plasma secondary PK endpoints include AUC(0-t), T_{max}, t_{lag}, CL/F, λ_z, and t_{1/2}, as data permit. Urine primary PK endpoints include AUC(0-48) and CL_r of gepotidacin, as data permit. Urine secondary PK endpoints include Ae(t₁-t₂), AUC(0-12), AUC(0-24), and AUC(0-48) of gepotidacin, as data permit
Model Specification

 The plasma T_{max} will be analyzed non-parametrically using the Mann Whitney U test (Wilcoxon rank sum test). The point estimates and 90% CI for the median differences will be derived for hepatic impairment and healthy participants based on Hodges-Lehmann estimation. The urine ln-transformed AUC(0-48) and non-transformed CL_r values for gepotidacin in the hepatic impairment groups and the normal hepatic function group will be compared using an analysis of variance (ANOVA).
Model Checking & Diagnostics

 Model assumptions will be applied, but appropriate adjustments may be made based on the data.
Model Results Presentation

 The point estimates and 90% confidence intervals for the median differences in plasma T_{max} will be calculated for the cohort difference (hepatically impaired – healthy participants). Statistical analysis by ANOVA will be presented in tabular format with geometric mean ratios between hepatic impairment groups and normal hepatic function group, and 90% CIs for the ratios of AUC(0-48) for gepotidacin. For non-transformed CL_r for gepotidacin, least squares mean difference between hepatic impairment groups and normal hepatic function group, and 90% CIs for the difference will be presented.

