
 To compare the urine PK parameters of a 1500 mg oral dose of gepotidacin in normal healthy participants with participants with mild, moderate, and severe hepatic impairment 	
 Urine primary PK endpoints include Ae total, fe%, and CLr of gepotidacin, as data permit. Urine secondary PK endpoints include Ae(t1-t2), AUC(0-12), AUC(0-24), and AUC(0-48) of gepotidacin, as data permit
Exploratory	

 To evaluate the saliva PK parameters of a 1500 mg oral dose of gepotidacin in normal healthy participants compared with participants with mild, moderate, and severe hepatic impairment 	
 Saliva primary PK endpoints include AUC(0-∞) and Cmax of gepotidacin, as data permit. Saliva secondary PK endpoints include AUC(0-t), Tmax, λz, t1/2, CL/F, Vz/F, and saliva to unbound plasma AUC(0-t) and AUC(0-∞) ratios (RAUC) of gepotidacin, as data permit

Overall Design:

This is a Phase I, nonrandomized, open-label, parallel-group, multi-center, two-part study that will evaluate the pharmacokinetics, safety, and tolerability of a single 1500 mg oral dose of gepotidacin in participants with normal hepatic function and in participants with mild, moderate, and severe hepatic impairment. Healthy participants with normal hepatic function will be matched to hepatically impaired participants in terms of gender distribution, age (approximately ±10 years), and body mass index (approximately ±20%).

At Screening, participants will be enrolled to the appropriate groups based on the classification as defined in the Food and Drug Administration Guidance for Industry, Pharmacokinetics in Patients with Impaired Hepatic Function: Study Design, Data Analysis, and Impact on Dosing and Labeling [DHHS, 2003]. Participants with hepatic impairment will be classified using the Child-Pugh system.

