The natural log-transformed urine AUC(0-48) and non-transformed CL_r values for gepotidacin in the hepatic impairment groups and normal hepatic function groups will be compared using an analysis of variance. Geometric mean ratios between hepatic impairment groups and normal hepatic function groups, and 90% CIs for the ratios of AUC(0-48) and least square mean difference between hepatic impairment groups and normal hepatic function groups, and 90% CIs for the difference of CL_r for gepotidacin will be presented.

Detailed descriptions of the analyses in this study will be presented in the Reporting and Analysis Plan (RAP).

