2.2. Study Objective(s) and Endpoint(s)

Objectives	Endpoints
Primary Objectives	Primary Endpoints

 To compare the plasma PK parameters of a 1500 mg oral dose of gepotidacin in normal healthy participants to participants with mild, moderate, and severe hepatic impairment 	
 Plasma gepotidacin AUC(0-∞) and Cmax, as data permit.
Secondary Objectives	Secondary Endpoints

 To assess the safety and tolerability of gepotidacin administered as a 1500 mg oral dose in normal healthy participants compared with participants with mild, moderate, and severe hepatic impairment To compare the secondary plasma PK parameters of 1500 mg oral dose of gepotidacin in normal healthy participants with participants with mild, moderate, and severe hepatic impairment To compare the urine PK parameters of a 1500 mg oral dose of gepotidacin in normal healthy participants with participants with 	
 12-lead safety ECG readings, change from baseline in vital sign measurements (blood pressure and heart rate), monitoring of AEs, toxicity grading of clinical laboratory test results, and physical examinations Plasma gepotidacin AUC(0-t), Tmax, tlag, CL/F, Vz/F, λz, and t1/2, as data permit Urine gepotidacin PK endpoints: 
 Primary: Ae total, fe %, and CLr, as data permit Secondary: Ae(t1-t2), AUC(0-12), AUC(0-24), and AUC(0-48), as data permit

Objectives	Endpoints
mild, moderate, and severe hepatic impairment	
Exploratory Objectives	Exploratory Endpoints

• To evaluate the saliva PK parameters of a 1500 mg oral dose of gepotidacin in normal healthy participants compared with participants with mild, moderate, and severe hepatic impairment	
• Saliva gepotidacin PK endpoints:
○ Primary: AUC(0-∞) and Cmax, as data permit○ Secondary: AUC(0-t), Tmax, λz, t1/2, CL/F, Vz/F, and saliva to unbound plasma AUC(0-t) and AUC(0-∞) ratios (RAUC) of gepotidacin, as data permit.

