10.8.6. Pharmacokinetic Tables

Pharmacokinetic : Tables					
No.	Population	IDSL / Example Shell	Title	Programming Notes	Deliverable
PK Concentration Data					
3.1	PK Concentration	PKCT1	Summary of Gepotidacin Plasma Pharmacokinetic Concentration-Time Data (units) by Hepatic Function Group		IA, SAC
3.2	PK Concentration	PKCT1	Summary of Gepotidacin Urine Pharmacokinetic Concentration-Time Data (units) by Hepatic Function Group		IA, SAC
3.3	PK Concentration	PKCT1	Summary of Gepotidacin Saliva Pharmacokinetic Concentration-Time Data (units) by Hepatic Function Group		IA, SAC
PK Parameters Tables					
3.4	PK Parameter	PKPT4	Summary of Derived Gepotidacin Plasma Pharmacokinetic Parameters by Hepatic Function Group	Parameters with units. If Group E are enrolled in part 2, then include a page of part 1 (Group B and D) alone in SAC deliverable as a reference for part 1 IA.	IA, SAC
3.5	PK Parameter	PKPT4	Summary of Derived Gepotidacin Urine Pharmacokinetic Parameters by Hepatic Function Group	Parameters with units.	IA, SAC
3.6	PK Parameter	PKPT4	Summary of Derived Gepotidacin Saliva Pharmacokinetic Parameters by Hepatic Function Group	Parameters with units.	IA, SAC

Pharmacokinetic : Tables					
No.	Population	IDSL / Example Shell	Title	Programming Notes	Deliverable
PK Analysis Tables					
3.7	PK Parameter	PKPT3	Statistical Analysis of Gepotidacin Plasma Pharmacokinetic Parameters: Analysis of Variance (ANOVA)	AUC(0-∞) and Cmax only by Hepatic Function Group. If Group E are enrolled in part 2, then include a page of part 1 (Group B and D) alone in SAC deliverable as a reference for part 1 IA.	IA, SAC
3.8	PK Parameter	PKPT3	Statistical Analysis of Gepotidacin Urine Pharmacokinetic Parameters: Analysis of Variance (ANOVA)	AUC(0-48) and CLr only by Hepatic Function Group.	IA, SAC
3.9	PK Parameter	PKPT3	Statistical Analysis of Gepotidacin Saliva Pharmacokinetic Parameters: Analysis of Variance (ANOVA)	AUC(0-∞) and Cmax only by Hepatic Function Group.	IA, SAC
3.10	PK Parameter	PK T1	Statistical Analysis of Gepotidacin Plasma Tmax		IA, SAC
3.11	PK Parameter	PK T1	Statistical Analysis of Gepotidacin Saliva Tmax		IA, SAC

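### SAP 7.2.4.1 puts urine AUC(0-48) in place of Ae total and fe% as primary urine endpoints, and those two get no modelled comparison between hepatic groups

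*SAP*

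**What the plan says.** The endpoint tables agree with each other. The protocol synopsis, repeated in Protocol Section 4, states "Urine primary PK endpoints include Ae total, fe%, and CLr of gepotidacin, as data permit". SAP 2.2 follows with "Primary: Ae total, fe %, and CLr, as data permit" and, at the next level, "Secondary: Ae(t1-t2), AUC(0-12), AUC(0-24), and AUC(0-48), as data permit".

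The methods section differs. SAP 7.2.4.1 states "Urine primary PK endpoints include AUC(0-48"), with CLr as the only other member, followed by "Urine secondary PK endpoints include Ae(t₁-t₂), AUC(0-12), AUC(0-24), and AUC(0-48) of gepotidacin, as data permit". AUC(0-48) thus appears at both levels there, and Ae total and fe% at neither.

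The modelled analysis is the same everywhere. Protocol 10.3.1 applies the ANOVA to "The natural log-transformed urine AUC(0-48") and to untransformed CLr. SAP 7.2.4.1 repeats this, and the note to Table 3.8 in SAP 10.8.6 reads "AUC(0-48) and CLr only by Hepatic Function Group".

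Ae total and fe% are derived in SAP 7.2.1.2, summarised by hepatic function group in Table 3.5 and listed in Listing 45. SAP Table 1 declares one change from the protocol, which concerns hypersensitivity listings.

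**The concern.** Two things are at stake.

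First, the SAP gives two different sets of primary urine endpoints. A programmer or report author cannot follow both SAP 2.2 and SAP 7.2.4.1, and the urine result presented as primary would depend on which section was read.

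Second, two of the three urine endpoints named as primary have no planned between-group estimate. The objective is a comparison, and SAP 2.4 commits to an estimation approach. The study rationale rests on how gepotidacin is eliminated: Protocol 3.1 puts unchanged drug in urine at about 20% of the oral dose, which is the quantity fe% measures. The parameter that gets the modelled ratio is an area under urine concentrations, which also reflects how dilute the urine is and how the collection periods were cut.

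**Working it through.** **1. Endpoint status by section**

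| Parameter | Protocol 1 and 4; SAP 2.2 | SAP 7.2.4.1 | Urine ANOVA (Protocol 10.3.1; SAP Table 3.8) |
|---|---|---|---|
| Ae total | primary | not listed | no |
| fe% | primary | not listed | no |
| CLr | primary | primary | yes, difference with 90% CI |
| AUC(0-48) | secondary | primary and secondary | yes, ratio with 90% CI |

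**2. Dependence of AUC(0-48) on urine volume**

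Concentration is amount divided by volume. At fixed amounts, an area under concentration therefore scales as 1/volume. The documents give no urine volumes, so the inputs here are assumed.

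- Amounts in 0–6, 6–12, 12–24, 24–36 and 36–48 h: 180, 70, 35, 10 and 5 mg. The sum is 300 mg, and fe% = 300/1500 × 100 = 20%.
- Volumes: 0.4, 0.4, 0.8, 0.8 and 0.8 L, giving 450, 175, 43.75, 12.5 and 6.25 mg/L.
- Linear trapezoids from zero through the interval midpoints (3, 9, 18, 30, 42 h): 675 + 1875 + 984.4 + 337.5 + 112.5 = 3984.
- All volumes halved: 7969. All volumes doubled: 1992.

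Ae total stays at 300 mg and fe% at 20% in all three cases.

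**3. Dependence of AUC(0-48) on the collection intervals**

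Impaired participants have 5 post-dose intervals and normal participants have 8 (Protocol Table 2 footnotes; SAP 10.1.2), so the trapezoids run on different grids in the two arms of the comparison. Take identical excretion and constant urine flow in both. Cumulative excretion is F(t) = 1 − (ka·e^(−ke·t) − ke·e^(−ka·t))/(ka − ke), with ke = ln 2/half-life, and interval concentration is proportional to [F(t2) − F(t1)]/(t2 − t1). Assume half-lives of 4 to 12 h and ka of 0.7, 1.0 and 1.5 per hour. The impaired/normal AUC(0-48) ratio is then 0.89 to 0.94 with concentrations placed at interval midpoints, and 0.93 to 0.94 with interval ends. The true ratio is 1, and the Ae total ratio is exactly 1.00, because a sum over 0–48 h does not depend on where it is cut.

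**4. The Ae formula**

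SAP 7.2.1.2 computes Ae(t1-t2) as urine concentration times interval length, with no volume. Applied literally to step 2, Ae total becomes 450×6 + 175×6 + 43.75×12 + 12.5×12 + 6.25×12 = 4500 mg·h/L. It becomes 9000 or 2250 when volumes are halved or doubled. That is not an amount, it depends on volume just as AUC(0-48) does, and it carries into fe% and CLr.

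**5. Precision of an added Ae total ratio**

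The plan's only precision figures are for plasma (Protocol 10.1). With s = sqrt(ln(1 + CV²)), the upper 90% limit lies exp(t(0.95, n1+n2−2) × s × sqrt(1/n1 + 1/n2)) − 1 above the ratio. For 8 against 8, t = 1.761, and CVb of 23.4%, 22.9% and 43.6% give 22.55%, 22.03% and 44.40%. The protocol states 22.5%, 22.0% and 44.4%, so the formula is the right one.

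No CVb is given for any urine parameter, so a range is assumed for Ae total:

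| Assumed CVb | 8 vs 8 | 6 vs 8 |
|---|---|---|
| 20% | 19.1% | 21.0% |
| 30% | 29.5% | 32.7% |
| 40% | 40.4% | 44.9% |
| 50% | 51.6% | 57.6% |
| 60% | 63.0% | 70.5% |

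At a common dose D, the fe% ratio is (Ae_imp/D)/(Ae_norm/D) = Ae_imp/Ae_norm, so one analysis serves both endpoints.

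**The case against.** A reader might infer that the SAP discarded all three primary urine endpoints, that it invented the AUC(0-48) analysis, or that Ae total and fe% are not compared at all. The documents support none of these.

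- CLr remains primary in SAP 7.2.4.1 and is modelled.
- The restriction of the ANOVA to AUC(0-48) and CLr is already in Protocol 10.3.1, and the SAP carries it out unchanged. SAP Table 1 lists changes to the planned analysis, and the modelled urine analysis did not change. What the SAP altered is the label.
- Table 3.5 summarises urine parameters by group at interim and final. SAP 10.3.3 gives geometric means with 95% CIs, and Ae total and fe% are not among the parameters exempted from ln-transformation. What is missing is a modelled contrast between groups.

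The consequence is also limited. These are sub-levels within a secondary objective, with no alpha or sample-size rule attached, and the numerical thresholds for enrolling the severe group are plasma AUC and Cmax.

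It can further be said that CLr covers the excretion question, since it is Ae total divided by plasma AUC. This does not hold. Ae total = CLr × plasma AUC, so if CLr were unchanged and plasma AUC rose by 50% (the itraconazole effect on AUC(0-∞) in Protocol 5.5, borrowed only for scale), the CLr difference would be 0 and the Ae total ratio 1.5.

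The other points stand and set the limits of the finding. They do not remove the contradiction between SAP 2.2 and SAP 7.2.4.1, or the absence of a ratio with CI for two declared primary urine endpoints.

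**Conclusion.** The point holds in a bounded form. SAP 7.2.4.1 contradicts SAP 2.2 and the protocol on which urine endpoints are primary: AUC(0-48) replaces Ae total and fe%, CLr is kept, AUC(0-48) is labelled twice, and the relabelling is undeclared. The gap in the modelled comparison predates the SAP, because the protocol's own endpoint and analysis sections do not match.

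The contradiction and the gap rest on the text alone. The size of the mismatch between AUC(0-48) and the amount excreted rests on assumptions: a twofold volume difference gives an AUC(0-48) ratio of 0.5 or 2.0 with no change in excretion, and the unequal grids alone give about 0.89 to 0.94 under the model used. Actual volumes and half-lives could give larger or smaller effects. The change should be made, but the plasma primary analysis is untouched.

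**What to change.** 1. In SAP 7.2.1.2, define Ae(t1-t2) as urine concentration times urine volume collected in the interval. This comes first, because Ae total, fe% and CLr all depend on it.
2. In SAP 7.2.4.1, list Ae total, fe% and CLr as primary urine endpoints and AUC(0-48) as secondary only, as in SAP 2.2.
3. Add an ln-scale ANOVA of Ae total to Table 3.8, with geometric mean ratio and 90% CI against normal hepatic function. State that the fe% ratio is identical at a common dose, and that fe% is to be analysed if dose differs between groups.
4. Keep the AUC(0-48) ANOVA as a secondary analysis. Dropping it would itself depart from Protocol 10.3.1.
5. Record the added analysis in SAP Table 1.

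The cost is SAP wording and one extra analysis row, with no new endpoint. Urine volume per interval has to be available in the data for step 1, but any valid Ae needs it already. If the sponsor prefers Ae total and fe% to stay descriptive, the minimum is to say so in 7.2.4.1, correct the labels and declare it in Table 1. The urine objective would then lack a modelled estimate for two of its primary endpoints.

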7.3. Exploratory Pharmacokinetic Analyses

7.3.1. Endpoint / Variables

7.3.1.1. Drug Concentration Measures

Refer to [Appendix 3: Data Display Standards & Handling Conventions \(Section 10.3.3 Reporting Standards for Pharmacokinetic\)](#)

7.3.1.2. Derived Pharmacokinetic Parameters

Pharmacokinetic parameters will be calculated by standard non-compartmental analysis according to current working practices and using the currently supported version of WinNonlin. All calculations of non-compartmental parameters will be based on actual sampling times. Pharmacokinetic parameters listed will be determined from the saliva concentration-time data, as data permits.

Parameter	Parameter Description
AUC(0-t)	Area under the concentration-time curve from time 0 (predose) to time of last quantifiable concentration, to be calculated using the linear trapezoidal rule for each incremental trapezoid and the log trapezoidal rule for each decremental trapezoid.
AUC(0-∞)	Area under the concentration-time curve from time 0 (predose) extrapolated to infinite time, calculated as: $AUC(0-\infty) = AUC(0-t) + C(t) / \lambda_z$
C _{max}	Maximum observed concentration, determined directly from the concentration-time data.
T _{max}	Time to first occurrence of C _{max}
t _{1/2}	Terminal phase half-life will be calculated as: $t_{1/2} = \ln 2 / \lambda_z$
λ _z	Terminal-phase rate constant
CL/F	The apparent oral clearance, calculated as: $CL/F = Dose / AUC(0-\infty)$
V _z /F	The apparent volume of distribution during the terminal phase, calculated as: $V_z/F = CL / \lambda_z$
RAUC(0-t)	The ratio of the AUC(0-t) observed in saliva relative to the unbound AUC(0-t) in plasma, calculated as: $RAUC(0-t) = AUC(0-t) \text{ saliva} / AUC(0-t) \text{ plasma}$
RAUC(0-∞)	The ratio of the AUC(0-∞) observed in saliva relative to the unbound AUC(0-∞) in plasma, calculated as: $RAUC(0-\infty) = AUC(0-\infty) \text{ saliva} / AUC(0-\infty) \text{ plasma}$

NOTES:

- Additional parameters may be included as required.
- Since plasma protein binding of gepotidacin is low (33%), only total plasma drug concentrations and total plasma PK parameters will be reported for the plasma PK analysis. However, to derive the saliva to unbound plasma AUC(0-t) and AUC(0-∞) ratios, a correction factor of 0.67 will be applied to the total plasma AUCs of gepotidacin to derive the unbound plasma AUCs.

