In Part 2, participants with mild (optional) and severe hepatic impairment and participants with normal hepatic function will be enrolled concurrently based on the PK, safety, and tolerability data of Part 1. Participants with mild hepatic impairment may be studied if there is a significant difference in pharmacokinetics between participants with moderate hepatic impairment and participants with normal hepatic function. Participants with severe hepatic impairment will be studied in Part 2 provided that the PK objectives are achieved in Part 1 (observed mean values in participants with moderate impairment do not exceed the threshold: AUC <48 µg•hr/mL and C_{max} <14 µg/mL). The dose may be adjusted for participants with severe hepatic impairment if either PK parameter is predicted to exceed the threshold. Based on emergent data from Part 1, matching

participants with normal hepatic function in Part 2 (Group E) may be enrolled (e.g., if a change in dose is needed or if the demographic data of the mild and/or severe hepatic impairment groups is not well matched to the moderate control data [Group D]) (see Section 7.3).

Due to the potential difficulty in identifying eligible participants with severe hepatic impairment, the sponsor may stop the study prior to full enrollment in Part 2 provided that a minimum of 6 evaluable participants with severe hepatic impairment have been enrolled. See the study schematic in Figure 1 for more details.

For participants with normal hepatic function and participants with mild, moderate, and severe hepatic impairment: participants will participate in 1 treatment period and blood, urine, and saliva samples will be collected for PK analysis of gepotidacin concentrations according to the Schedule of Activities (SoA; Section 2). Blood, urine, and saliva samples will be collected up to approximately 48 hours after dosing.

Figure 1 BTZ117352 Study Schematic

PK = pharmacokinetic

- ¹ Based on emergent data from Part 1, participants with mild hepatic impairment (Group A) may not be enrolled in Part 2 if there is not a significant difference between participants with moderate hepatic impairment and participants with normal hepatic function.

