10.3.3. Reporting Standards for Pharmacokinetic

Pharmacokinetic Concentration Data	
Descriptive Summary Statistics, Graphical Displays and Listings	
Refer to IDSL PK Display Standards. Refer to IDSL Statistical Principle 6.06.1.
 
For continuous data:
 
 NQs at the beginning of a participant profile (i.e. before the first incidence of a measurable concentration) are deemed to be zero as it is assumed that in this circumstance no drug is yet measurable in the blood. For NQs at the end of the participant profile (i.e. after the last incidence of a measurable concentration); 
 for individual plots and pharmacokinetic analyses these are dropped (set to missing) as they do not provide any useful information (and can erroneously indicate that absolutely no drug is present) for summary statistics, these are set to 0 (to avoid skewing of the summary statistics) Individual NQs which fall between two measurable concentrations are set to missing (individual values of this nature are assumed to be an anomaly) 
If two or more NQ values occur in succession between measurable concentrations, the profile will be deemed to have terminated at the last measurable concentration prior to these NQs. For the purpose of individual participant plots, these NQs will be set to 0, and the subsequent measurable concentrations will be retained. For the derivation of pharmacokinetic parameters, these NQs and any subsequent measurable concentrations will be omitted (set to missing).
 
Note: Concentration values will be imputed as per GUI_51487 for descriptive summary statistics/analysis and summarized graphical displays only.

Pharmacokinetic Parameter Data	
Descriptive Summary Statistics, Graphical Displays and Listings	
N, n, geometric mean, 95% CI of geometric mean, standard deviation (SD) of logged data and between geometric coefficient of variation (CV_b (%)) will be reported.
 $CV_b (\%) = \sqrt{(\exp(SD^2) - 1) * 100}$ 
(SD = SD of Ln-Transformed data)

Parameters Not Being Ln-Transformed	T _{max} , t _{lag} , CL _r , lambda _{z_lower} , lambda _{z_upper} , and lambda _{z_no.} of points.
Parameters Not Being Summarized	lambda _{z_lower} , lambda _{z_upper} , and lambda _{z_no.} of points.
Listings	Include the first point, last point and number of points used in the determination of λ _z and R _{sq_adjusted} for listings.

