10.8.7. Pharmacokinetic Figures

Pharmacokinetic : Figures					
No.	Population	IDSL / Example Shell	Title	Programming Notes	Deliverable
Concentration Plots					
3.1	PK Concentration	PKCF1P	Individual Gepotidacin Plasma Concentration-Time Plots by Hepatic Function Group (Linear and Semi-Logarithmic)	Dashed line represents the LLQ. Present all hepatic function groups in the same plots.	IA, SAC
3.2	PK Concentration	PKCF1P	Individual Gepotidacin Urine Concentration-Time Plots by Hepatic Function Group (Linear and Semi-Logarithmic)	Dashed line represents the LLQ. Present all hepatic function groups in the same plots. Plot concentration at the collection midpoint.	IA, SAC
3.3	PK Concentration	PKCF1P	Individual Gepotidacin Saliva Concentration-Time Plots by Hepatic Function Group (Linear and Semi-Logarithmic)	Dashed line represents the LLQ. Present all hepatic function groups in the same plots.	IA, SAC
3.4	PK Concentration	PKCF2	Mean Gepotidacin Plasma Concentration-Time Plots (Linear and Semi-Logarithmic)	Dashed line represents the LLQ. Present all treatment groups in the same plots.	IA, SAC
3.5	PK Concentration	PKCF2	Mean Gepotidacin Urine Concentration-Time Plots (Linear and Semi-Logarithmic)	Dashed line represents the LLQ. Present all treatment groups in the same plots. Plot concentration at the collection midpoint.	IA, SAC
3.6	PK Concentration	PKCF2	Mean Gepotidacin Saliva Concentration-Time Plots (Linear and Semi-Logarithmic)	Dashed line represents the LLQ. Present all treatment groups in the same plots.	IA, SAC

Pharmacokinetic : Figures					
No.	Population	IDSL / Example Shell	Title	Programming Notes	Deliverable
3.7	PK Concentration	PKCF3	Median Gepotidacin Plasma Concentration-Time Plots (Linear and Semi-Logarithmic)	Dashed line represents the LLQ. Present all treatment groups in the same plots.	IA, SAC
3.8	PK Concentration	PKCF3	Median Gepotidacin Urine Concentration-Time Plots (Linear and Semi-Logarithmic)	Dashed line represents the LLQ. Present all treatment groups in the same plots. Plot concentration at the collection midpoint.	IA, SAC
3.9	PK Concentration	PKCF3	Median Gepotidacin Saliva Concentration-Time Plots (Linear and Semi-Logarithmic)	Dashed line represents the LLQ. Present all treatment groups in the same plots.	IA, SAC
Exploratory Objectives					
3.10	PK Concentration	PK_F4	Scatter Plot of Gepotidacin Saliva and Unbound Plasma Concentrations by Hepatic Function Group	Present all treatment groups in the same plots.	IA, SAC

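### RAUC(0-t) sets no common end time for saliva and plasma, so the ratio can compare different time windows when their last quantifiable samples differ

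*SAP*

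**What the plan says.** SAP 7.3.1.2 gives saliva AUC(0-t) as "Area under the concentration-time curve from time 0 (predose) to time of last quantifiable concentration". SAP 7.2.1.2 uses the same definition for plasma, and Protocol 10.3.1 and 10.3.3 agree. RAUC(0-t) is "The ratio of the AUC(0-t) observed in saliva relative to the unbound AUC(0-t) in plasma", where "a correction factor of 0.67 will be applied to the total plasma AUCs of gepotidacin to derive the unbound plasma AUCs".

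SAP 10.3.3 determines where each profile ends. For non-quantifiable (NQ) values after the last measurable one, "for individual plots and pharmacokinetic analyses these are dropped (set to missing) as they do not provide any useful information". If two or more NQ values occur in succession between measurable ones, "the profile will be deemed to have terminated at the last measurable concentration prior to these NQs". Both rules work on a single profile.

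Protocol 5.1 states: "Blood, urine, and saliva samples will be collected up to approximately 48 hours after dosing". Protocol Table 2 gives blood and saliva the same nominal times from predose to 48 h. SAP 10.8.7 refers to an assay limit for the plots ("Dashed line represents the LLQ"), but neither document gives its value for plasma or saliva.

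**The concern.** A ratio of two areas measures saliva/plasma partitioning only if both areas cover the same period. Here each area stops where its own assay stops detecting drug, and no rule covers unequal stopping times. The other cross-matrix parameter does have such a rule: for renal clearance, SAP 7.2.1.2 ties the plasma AUC to the urine collection period.

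The stopping time depends on assay sensitivity, on exposure and on the terminal decline, and the last two may change with hepatic function. Saliva parameters are summarised by hepatic function group at both the interim and the final analysis (SAP Table 3.6). A reader could therefore take a difference in RAUC(0-t) between groups as a difference in partitioning when it only reflects where the profiles were cut.

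**Working it through.** **Figures in the plan.** There is none for RAUC. The only design figures, the upper 90% confidence limits in Protocol 10.1, concern plasma ratios and do not enter here. They do reproduce: exp(t(0.95, 14 df) × √ln(1+CV²) × √(2/8)) − 1 gives 22.55%, 22.03% and 44.40%, against the stated 22.5%, 22.0% and 44.4%.

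**Step 1: what the definition implies.** Suppose saliva is a constant multiple R of unbound plasma, so that a correct ratio equals R. Let saliva end at tS and plasma at tP, with tS ≤ tP. Then

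RAUC(0-t)/R = [R × 0.67 × AUCp(0-tS)] / [0.67 × AUCp(0-tP)] / R = AUCp(0-tS) / AUCp(0-tP).

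The 0.67 cancels. The result is 1 if tS = tP and below 1 if saliva ends first. If plasma ended first, the ratio would be too high.

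**Step 2: illustration on the planned sampling times.** From the documents: the sampling times in Protocol Table 2, the linear-up/log-down trapezoidal rule and the dropping of trailing NQ values. Assumed: highest sampled plasma value 7 µg/mL, absorption rate 1.5 per h, first-phase half-life 2.5 h, terminal half-life 8, 12 or 16 h with 5% terminal weight, R = 0.5 or 1, plasma limit 0.01 µg/mL, saliva limit 0.01 to 0.5 µg/mL. Plasma AUC(0-t) is then 40.5, 43.3 and 45.3 µg·h/mL, below the protocol's threshold of 48.

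| Terminal half-life | Plasma ends | RAUC(0-t)/R, saliva to 24 h | to 12 h | to 8 h |
|---|---|---|---|---|
| 8 h | 36 h | 0.986 | 0.907 | 0.806 |
| 12 h | 48 h | 0.958 | 0.861 | 0.760 |
| 16 h | 48 h | 0.937 | 0.828 | 0.728 |

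The ratio is about 1-6% too low at 24 h, 9-17% at 12 h and 19-27% at 8 h. With saliva to 36 h and plasma to 48 h (16 h half-life) it is 0.977. With equal last times, or with both areas cut at the earlier one, it is 1.000 in every scenario.

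**Step 3: sensitivity to the late tail.** With 20% terminal weight and plasma to 48 h, the same half-lives give 0.947, 0.889 and 0.843 for saliva to 24 h, and 0.808, 0.715 and 0.652 for 12 h. Those profiles have plasma AUCs of 51.1, 60.5 and 68.0 µg·h/mL, all above 48.

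The extreme is mono-exponential decline, (1 − 2^(−tS/h)) / (1 − 2^(−48/h)). For h = 6, 10 and 14 h it gives 0.941, 0.841 and 0.766 at 24 h, and 0.753, 0.586 and 0.494 at 12 h. These half-lives imply AUC/Cmax = h/ln 2 of about 8.7, 14.4 and 20.2 h. The protocol's thresholds give 48/14 = 3.4 h, and the Step 2 profiles 40.5/7 = 5.8 to 45.3/7 = 6.5 h. The thresholds are limits on means, not a profile, so this comparison is only indicative.

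**Step 4: groups.** Take the Step 2 profiles with R = 1 and a saliva limit of 0.1 µg/mL. Half-lives of 8, 12 and 16 h then give 0.907, 0.861 and 0.937, because saliva ends at 12, 12 and 24 h and plasma at 36, 48 and 48 h. The 16 h to 12 h contrast is 0.937/0.861 = 1.09, about 9% with identical partitioning. The sequence falls and then rises.

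**The case against.** **The mismatch may never occur.** Blood and saliva share the same nominal times, so if both are quantifiable at the same last sample the windows match. A reader might infer that RAUC(0-t) necessarily compares different spans. The documents do not support that: without assay limits, half-life or saliva levels, a mismatch is possible but not shown. This stands.

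**The large figures are not realistic.** A reader might carry away errors of 25-51% for saliva ending at 12 h. Those come from the mono-exponential assumption, which puts far more area late in the profile than the protocol's thresholds suggest. This also stands.

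**Higher exposure need not favour impaired participants.** One might infer that impaired groups stay quantifiable longer in saliva and so show a higher ratio. Higher exposure prolongs plasma quantifiability too, and Step 4 is not monotone. Neither the direction nor the size of a group effect is established.

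**RAUC is of low rank and has companions.** It is a secondary saliva parameter under an exploratory objective. The saliva ANOVA table covers AUC(0-∞) and Cmax only (SAP Table 3.9), and the Part 2 rules rest on plasma exposure and the Part 1 safety review. RAUC(0-∞) and the saliva-plasma concentration scatter plots are also planned, and Listings 41 and 43 would allow a common-window ratio later. All this limits the importance. RAUC(0-∞) is not a full safeguard, though. In the Step 2 profiles, extrapolating from a saliva cut at 8 to 12 h with the true terminal rate overstated it by about 8% to 52%; a rate fitted to the shortened saliva profile would give a different error.

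**Conclusion.** The gap in the definition is real: RAUC(0-t) has no common end time, and the NQ rules can shorten one matrix and not the other. The ratio is distorted whenever the two last times differ in a participant, and is unaffected when they coincide.

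Size can only be illustrated. Under biexponential decline with 5% terminal weight and constant partitioning, the ratio is about 1-6% too low if saliva ends at 24 h and about 9-17% if it ends at 12 h. An earlier cut or a heavier late tail gives more, with mono-exponential decline as the worst case. Assay limits, half-lives, tail weight and saliva levels are all assumptions.

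The consequence is small. No primary endpoint, ANOVA or enrolment decision uses RAUC, and the exposure is limited to a descriptive by-group summary that could be misread. This is a worthwhile clarification rather than a necessary correction.

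**What to change.** Add one sentence to SAP 7.3.1.2: for RAUC(0-t), the saliva AUC and the unbound plasma AUC are both computed in each participant to the earlier of the two last quantifiable times. List that time with both matrices' last times. RAUC(0-∞) and the separately reported AUC(0-t) values stay as they are.

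The cost is that sentence, a partial-area calculation in WinNonlin and extra listing columns. No new samples or data are needed, and nothing changes where the last times already agree.

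There are two drawbacks. Some quantifiable late data in the longer matrix are not used for this ratio. The window also still varies between participants, so values are fully comparable only if partitioning is roughly constant over time. A fixed interval for all participants would be a legitimate alternative where both matrices are quantifiable throughout it.
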